**Primary Aim: To determine whether administration of oral LEV over two weeks modulates hippocampal hyperactivity**

Hypothesis 1: Oral LEV will decrease, in a dose-response relationship, hippocampal activity in healthy control subjects and psychotic patients (ASL study).

Hypothesis 2: Oral LEV will normalize hippocampal recruitment in patients (Scene-processing fMRI study).

Hypothesis 3: Compared with healthy control subjects, psychotic patients will show higher hippocampal activity (ASL study) and reduced hippocampal recruitment (Scene-processing fMRI study).

**Secondary Aim: To determine whether administration of oral LEV over two weeks improves clinical symptoms in patients with psychotic disorders**

Hypothesis 1: Oral LEV will improve cognitive symptoms in psychotic patients (eye-tracking relational memory task).

Hypothesis 2: Oral LEV will reduce positive and negative psychotic symptom severity (Positive and Negative Syndrome Scale, PANSS).

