**6.4 Cognitive Assessment:** Subjects will be asked to complete a relational memory experimental study. Subjects will be taken to a private interview room in the offices of the Psychiatric Neuroimaging Program. Eye tracking equipment will be used during the study to record eye movement behavior (ISCAN, Inc.). The eye tracking system uses a headmounted camera to track the subject's pupils in relation to a computer screen placed in front of the subject. Subjects will be shown the eye tracking system and given a brief explanation of the headmounted camera. The camera will be placed on the subject's head and the system software will be calibrated to the individual's pupil according to software specifications. Software may be recalibrated between each block of images to ensure accurate eye tracking. Subjects will view face and scene image pairs on a computer screen while eye movements are tracked. Faces and scenes will be drawn from a standard set of images which have been used in similar research studies (Hannula et al., 2010). Faces and scenes will be shown in color. Faces and scenes used are considered neutral, in that they should not elicit strong emotions (i.e., fear, anxiety, happiness). Subjects will be told to study each face/scene pair so that they can later identify a match between a particular face and scene. Subjects will view multiple blocks of face/scene pairs during the familiarization phase. During the testing phase, subjects will be shown blocks of previously seen scene images with multiple faces overlaid on the image. Subjects will be asked to choose the face previously related to the scene by button press while eye movements are tracked. Subjects will be fully debriefed following completion of all test phase blocks. Faces and scenes will be randomized to lists, and lists will be rotated and counterbalanced across subjects to ensure that each scene is paired equally with each face across the study. The relational memory experimental paradigm will require up to 1 hour, including calibration of the eye tracking software. There will be a total of two cognitive assessments in this study (baseline assessment and after two-week intervention).

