**6.6 Study Drug Administration:** After completing the baseline clinical assessment, cognitive assessment, and MRI, eligible participants will be instructed to take their first dose of 500 mg LEV. After a two hour time window, the participants will complete the same MRI battery. After the second MRI, patients will begin a 2-week intervention with 250 mg BID oral LEV. Clinical assessment, cognitive assessment, and MRI will be repeated after this 2-week intervention phase.

**6.6.a Dosage Rationale:** We selected 250 mg BID dosage because of other studies that have been able to safely demonstrate changes in cognitive performance and changes in hippocampal activation (Bakker et al., 2015, 2012) using dosages of LEV intervention in patient cohorts outside the FDA-approved indications for LEV. This dosage is well below the typical ranges for efficacy as an antiepileptic with doses of 1,000-3,000 mg/day. Studies using a dosage of 125 mg BID have reported drug levels to be 4.4 mcg/ml +/- 0.53 (mean and SEM), while dosages of 1,000-3,000 mg/day achieve levels of 10-40 mcg/ml (Bakker et al., 2015, 2012; Lyseng-Williamson, 2011). Human results indicating effects with lower dosages are consistent with the animal literature. Studies that have targeted rats with cognitive impairment and excess hippocampal activity have demonstrated improvements in memory performance using a dosage of 10 mg/kg (Koh et al., 2018, 2010). In another animal model of schizophrenia, dosages of 10 mg/kg improved a sensory gating task performance (Smucny et al., 2015). Typical antiepileptic doses of LEV in rodent seizure models are in a range of 50-150 mg/kg (Ji-Qun et al., 2005; Stratton et al., 2003).

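### Section 6.4 does not defer the full debriefing to the second memory assessment, so as written it falls between baseline and the on-LEV measurement

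*Combined protocol and SAP*

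**What the plan says.** Section 6.4 (Cognitive Assessment) describes one relational memory session in order: eye-tracker set-up and calibration, familiarization with face/scene pairs, then test blocks. At the end of that sequence it states: "Subjects will be fully debriefed following completion of all test phase blocks". It does not say what the debriefing covers or which session it follows.

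The same section says: "There will be a total of two cognitive assessments in this study (baseline assessment and after two-week intervention". Section 6.6 confirms the repeat: "Clinical assessment, cognitive assessment, and MRI will be repeated after this 2-week intervention phase". The outcome is the subject of Secondary Aim, Hypothesis 1, in section 2.0: "Oral LEV will improve cognitive symptoms in psychotic patients (eye-tracking relational memory task".

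Section 6.4 also shows what participants know before any debriefing:

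- **The memory aim:** "Subjects will be told to study each face/scene pair so that they can later identify a match between a particular face and scene".
- **The equipment:** "Subjects will be shown the eye tracking system and given a brief explanation of the headmounted camera".
- **The response at test:** "Subjects will be asked to choose the face previously related to the scene by button press while eye movements are tracked".

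Section 11.2.c plans analyses of variance and linear mixed models, within and across diagnostic groups and time points. It has no term or comparison for retest gain.

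**The concern.** The debriefing sentence sits inside the description of a single session and is tied to the end of that session's blocks. Staff following it as written would debrief at baseline, two weeks before the on-drug measurement. A full debriefing might explain what the eye movements are used for, and looking behaviour is partly under voluntary control.

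This matters because of the design. In patients, the second assessment is always on LEV, so time and drug coincide. Any non-drug change between the sessions, from whatever source, enters the estimate for Secondary Hypothesis 1 as if it were drug effect. A debriefing between the sessions is one such source, and it can be avoided.

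**Working it through.** **1. Does the debriefing fall between the two measurements?** Section 6.4 gives a session that ends in debriefing and says there are two such assessments. Section 6.6 places the second after the two-week intervention. No sentence limits the debriefing to the final session. The plain reading is that it follows each session, including baseline. A final-session-only reading is possible but not stated.

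**2. What could it add?** Before and during the baseline test, participants learn that they must remember pairings, that a camera tracks their eyes, and that they must pick the matching face. What section 6.4 does not say they are told is how gaze is used or scored. That is the most a debriefing could add. To look at the matching face on purpose, a participant must still remember or guess which face it is, and knowing the scoring supplies no memory for the button press. The documents do not say whether gaze or button-press accuracy is the scored outcome.

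**3. Where would a shift go?** Let L be the LEV effect on the change score and δ any non-drug shift, with subscripts P for patients and C for controls.

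- Pre-post change in patients: L_P + δ_P. The two parts cannot be separated.
- Group-by-time contrast if both groups take LEV: (L_P + δ_P) − (L_C + δ_C). If δ_P = δ_C, the shift cancels and L_P − L_C remains. That is a difference between groups in response, not LEV against no LEV.
- Group-by-time contrast if controls do not take two weeks of LEV: L_P + δ_P − δ_C, which equals L_P only if the shifts are equal.

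Which case applies is unclear. Section 2.0 has participants in general beginning two weeks of LEV after the second scan. Section 6.6 has patients beginning it. These passages must be reconciled.

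**4. Scale, for illustration.** The plan gives no figure for the memory task. The 80.3% power in section 11.3 concerns hippocampal activity and plays no part here.

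Inputs: n = 20 patients (analyzable target, section 5.3) or n = 30 (recruitment ceiling, section 5.3); α = 0.05 (section 11.3, sidedness not stated, taken as two-sided); a paired t-test on change; no LEV effect. The shift d, in SDs of the within-person change, is an assumption. No passage ties any value of d to debriefing.

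Formula: P(significant improvement) = P(T > t₀.₉₇₅,ₙ₋₁), where T is noncentral t with n − 1 degrees of freedom and noncentrality d√n. For n = 20 the critical value is 2.093; at d = 0.2 the noncentrality is 0.2 × √20 = 0.894, which gives 13.3%.

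| Assumed d | n = 20 | n = 30 |
|---|---|---|
| 0 | 2.5% | 2.5% |
| 0.1 | 6.2% | 7.6% |
| 0.2 | 13.3% | 18.4% |
| 0.3 | 24.6% | 35.5% |
| 0.5 | 56.4% | 75.4% |

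These are improvement-tail probabilities only. They describe any non-drug gain, whether from practice, reused lists or debriefing. They show how exposed an uncontrolled comparison is, not how much a debriefing contributes.

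**The case against.** The strongest reply is that the link from debriefing to apparent benefit is thin. The timing is inferred, the content is unknown, and participants already know the memory aim, the correct target and that gaze is recorded. Deliberate looking still depends on remembering the match. Simply completing the baseline session teaches the task, so ordinary retest gain is probably the larger problem. On materials, section 6.4 says only that "lists will be rotated and counterbalanced across subjects to ensure that each scene is paired equally with each face across the study", which is counterbalancing across subjects and does not establish that each person gets a different list at the second session. Deferring the debriefing touches neither issue.

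Most of this stands, and it limits the point to a small one. It does not remove it: the sentence as written still directs a debriefing before the second measurement, and a larger bias elsewhere is no reason to keep an avoidable one.

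A reader might go further and infer that participants will be told that looking at the matching face is the measure, and that a debriefing effect will therefore pass for LEV benefit. The documents do not support that. They do not describe the debriefing's content, name the scored outcome, or give any basis for the size or direction of an effect. Nor is it right that such a shift could never be separated from drug effect: one common to both groups cancels in the group-by-time contrast, although that contrast tests LEV against no LEV only if controls are untreated.

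**Conclusion.** The point holds as a minor design improvement. Section 6.4 leaves the debriefing undeferred, and on its plain reading participants are debriefed between the two measurements behind Secondary Hypothesis 1. With no placebo or clearly untreated comparison, any shift this caused would be credited to LEV in the pre-post change.

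The size cannot be computed from the documents. My judgement that it is small, and smaller than ordinary retest gain, rests on how much participants already know. The conclusion assumes that the debriefing follows the baseline session and conveys something about gaze that participants did not already have. If the sponsor intends debriefing only at the end, the text needs to say so. The primary imaging aim is not affected.

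**What to change.** Replace the debriefing sentence in section 6.4 with: *Subjects will be debriefed after the second (two-week) cognitive assessment, or at withdrawal; after the baseline assessment staff give no feedback on performance or on how eye movements are used.*

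The cost is one sentence and a two-week wait for the debriefing. Participants who withdraw still receive it.

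This does not remove ordinary practice effects. In the same edit it would help to state whether a different list is used at each session and which task measure is the outcome. Separately, sections 2.0 and 6.6 should be reconciled on who takes the two weeks of LEV, because that decides what the group-by-time contrast can show.

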**6.8 Urine pregnancy test:** All females will be required to take a urine pregnancy test during the screening and enrollment visit, baseline visit, and two-week follow-up visit, as addressed in the study drug risks below.

**6.9 Mid-Intervention Phone Call:** After the visit where LEV is administered and before the two week follow-up visit, we will call the participant. This will be to **1)** ensure that they are taking the study medication as prescribed and remind them to continue to do so. **2)** Ask about any issues or side effects they may be experiencing because of the study. We believe this phone call will increase the likelihood that participants complete the study and will help us identify any side effect complications earlier.

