## **7.0 RISKS - STUDY DRUG**

---

**7.1 Risks:** Side effects of LEV exposure have been well characterized in clinical trials using LEV dose ranges of 1000-3000 mg/day. The most common symptoms are neurological, including somnolence (15% of patients), asthenia (15%), headache (14%), dizziness (13%), and ataxia (3%) (Ben-Menachem and Falter, 2000; Cereghino et al., 2000; Shorvon et al., 2000). Patients also reported a slightly higher incidence of infection (13% of patients). Up to 13% of patients also experienced adverse neuropsychiatric symptoms. In most of these patients, the symptoms have been mild, including agitation, hostility, apathy, anxiety, emotional lability, and depression (Gambardella et al., 2008). About 1% of patients have experienced serious neuropsychiatric symptoms including hallucinations, suicidal ideations, or psychosis (Kossoff et al., 2001; Mula et al., 2003). In these reports, symptoms occurred mostly within the first month of therapy. Dose reduction or discontinuation has led to resolution of symptoms in cases reported. Conversely, LEV has no major adverse effects on cognitive function (Neyens et al., 1995), which is an improvement over more traditional anti-epileptic agents (Dooley and Plosker, 2000). Presently, there are no sufficient data to recommend treatment with LEV during pregnancy. Case reports have indicated Stevens-Johnson Syndrome (SJS) is an exceedingly rare side effect of LEV administration (Zou et al., 2012). In a meta-analysis of 26 double-blind, randomized, placebo-controlled trials (2832 patients), no dose-response relationship was found for any side effects (Verrotti et al., 2015).

**7.2 Absorption and Distribution:** LEV is rapidly and almost completely (>95%) absorbed (Rossetti and Bromfield, 2005) after oral administration of doses ranging from 250 to 5000 mg, with peak serum concentrations occurring approximately 1 hour after dose and steady state concentrations are reached within 48 hours (Gambardella et al., 2008). The oral bioavailability of LEV tablets is 100%. Food does not affect the absorption of LEV. The volume of distribution is 0.5-0.7 L/kg (Patsalos, 2004). LEV does not bind to plasma proteins and has linear pharmacokinetics that are time-invariant with low intra- and inter-subject variability (Patsalos, 2004, 2000).

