## **9.0 REPORTING OF ADVERSE EVENTS OR UNANTICIPATED PROBLEMS INVOLVING RISK TO PARTICIPANTS OR OTHERS**

---

We define an adverse event as any adverse change in health or development of a side effect occurring in a study participant after enrollment. These may be expected events (known drug effects, as detailed in the consent form, safety monitoring plan, or package insert) or unexpected events. The PI and Co-investigators will review any AE's that occurred during a participant's study experience, and determine their magnitude and causal attribution using the scale below. Every six months the PI and Co-investigators will review the magnitude and frequency of AE's and report such information to the IRB.

AE's of grade three or higher in the scale below will be reported immediately to the IRB using the Report of Adverse Events form and to the Program Director of the appropriate funding agency. In conjunction with the IRB, the PI then will determine if modifications to the protocol are warranted.

The primary method for ensuring data accuracy and protocol compliance will be the involvement of the PI in all aspects of the project. The PI and IRB have the authority to stop or modify the study at any time. During the semi-annual reviews, the PI and IRB will together decide if the study should continue unchanged, be modified, or closed to further enrollment.

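### The one scheduled contact during dosing asks only about problems the participant blames on the study, which is narrower than the protocol's own adverse event definition

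*Combined protocol and SAP*

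**What the plan says.** Section 6.9 provides one contact during dosing: "After the visit where LEV is administered and before the two week follow-up visit, we will call the participant". The first purpose is adherence. The second is: "Ask about any issues or side effects they may be experiencing because of the study". The protocol expects that the call "will help us identify any side effect complications earlier". It names no other contact between the first-dose visit and the two-week visit.

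Section 9.0 is wider. An adverse event is "any adverse change in health or development of a side effect occurring in a study participant after enrollment". The principal investigator and co-investigators review events and "determine their magnitude and causal attribution using the scale below". That scale has five levels, from definite to unrelated.

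Section 7.1 reports, from trials at 1000-3000 mg/day: "Up to 13% of patients also experienced adverse neuropsychiatric symptoms". It adds: "About 1% of patients have experienced serious neuropsychiatric symptoms including hallucinations, suicidal ideations, or psychosis". Onset in those reports was mostly in the first month.

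Section 6.3 provides PANSS, HAM-D with an in-house suicidality measure, and the VANRS side-effect scale, at baseline and after two weeks. The section applies to patients with psychosis only. Section 10.0 allows withdrawal at any time and states no safety assessment on leaving.

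**The concern.** Sections 6.9 and 9.0 put the decision about cause in different hands. Under 9.0 the investigators make it, after the event is known. Under 6.9 the participant makes it first, because the question covers only what they put down to the study.

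This matters more than usual here. Hallucinations, psychosis, suicidal thoughts, hostility and depression appear in 7.1 as effects of the drug, and they are also symptoms the enrolled patients may already have. A patient who hears more voices in the first week and blames the illness can truthfully answer no. The event then never reaches the attribution scale.

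At stake are the completeness of the adverse event record, which informs the six-monthly decision to continue, modify or close enrolment (section 9.0), and the earlier identification of complications that 6.9 gives as a reason for the call. There is no placebo arm against which under-reporting would show.

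**Working it through.** The plan gives no figure to reproduce. The check is a comparison of sections, followed by arithmetic for scale.

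**1. What the question elicits, against what section 9.0 requires**

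| Event during dosing | Asked about in 6.9 | Adverse event under 9.0 |
|---|---|---|
| Participant blames the drug or study | Yes | Yes |
| Participant blames the illness or something else | No | Yes |

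The second row is the gap. The two lowest levels of the section 9.0 scale (not likely, unrelated) have a use only if such events reach the investigators.

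**2. Other routes by which an event in that row could be found**

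- *Patient completes and worsening persists.* The section 6.3 scales would measure it at two weeks, whatever the patient thinks caused it. Detection is late rather than absent.
- *Episode settles before the two-week visit.* Nothing is rated at the time. The section 6.0 overview says that many measures look back over an interval, with two weeks as its example, but does not say which. Recall may recover some episodes; the plan does not secure it.
- *Patient withdraws early.* No exit assessment is stated.
- *Healthy control.* The section 6.3 scales do not apply. The call is the only side-effect enquiry described during dosing.
- *Score to adverse event.* No rule links a worse PANSS or HAM-D score to an adverse event entry. Section 6.3.a sends suicidal thoughts found at interview to treatment providers or clinic procedures, and states no adverse event entry.

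**3. Scale**

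Inputs: up to 30 patients and up to 30 controls (section 5.3); up to 13% with any neuropsychiatric symptom and about 1% with serious ones (section 7.1).

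- Any symptom, upper figure: 30 × 0.13 = 3.9 patients; 60 × 0.13 = 7.8 participants.
- At least one serious event occurring: 1 − (1 − 0.01)^n. For n = 30: 1 − 0.99^30 = 0.260. For n = 20: 0.182. For n = 60: 0.453.

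These are chances of occurrence. The number withheld at the call depends on the share of patients who blame their illness, which the documents do not give. Purely as an assumption, shares of 25%, 50% and 75% would withhold 3.9 × 0.25 = 1.0, 3.9 × 0.50 = 2.0 and 3.9 × 0.75 = 2.9 patients' reports, if every event began before the call.

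**4. Timing**

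No day is set. Of 14 dosing days, a call on day 1 leaves 13 after it, on day 7 leaves 7, and on day 13 leaves 1.

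**The case against.** The strongest reply is that the events of most concern do not depend on the call. Psychosis and suicidality are rated with PANSS, HAM-D and the suicidality measure after two weeks. This stands for patients who complete with persisting symptoms, so a reader should not infer that worsening psychosis will simply go unseen.

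A reader might also infer that patients lose more reports than controls, who have no illness to blame. The documents do not support this. Controls receive none of the section 6.3 scales, so they have fewer structured ways for a symptom to be found, and the net direction could be the reverse.

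On timing, 6.9 is titled as a mid-intervention call. A call on the first evening or on day 13 fits the sentence but not the title, so the missing window is a matter for clarification and does not show that the call fails its purpose.

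The sentence may also summarise a broader script, and section 9.0 refers to a safety monitoring plan and a consent form that are not available here. That is fair. Even so, the protocol text is what a caller is bound to, and it does not match section 9.0.

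Finally, no listed aim tests safety and section 11 plans no adverse event analysis, so no planned hypothesis test is compromised. What remains is the completeness of the record used to oversee the study.

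**Conclusion.** The concern holds in a limited form. The safety question in 6.9 is narrower than the adverse event definition in 9.0 and lets participant attribution come before investigator attribution, for risks that overlap with the patients' illness. The two-week ratings cover part of the gap, late. Transient episodes, early withdrawals and healthy controls are left without assured capture, and no rule converts scores into adverse events.

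For size, up to 3.9 of 30 patients would have neuropsychiatric symptoms, with a 26% chance of at least one serious event. Three limits apply:

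- The 13% is an upper figure, not a point rate.
- Both rates come from 1000-3000 mg/day, while this study gives 250 mg twice daily after a first 500 mg dose. That they carry over is an assumption, as is their application to two weeks of dosing, since section 7.1 gives no observation period. Section 7.1 does cite a meta-analysis that found no dose-response for side effects.
- The 26% is the chance that a serious event occurs. A reader might take it as the chance that one is missed, which the documents do not allow anyone to calculate.

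The mismatch between 6.9 and 9.0 depends on none of these figures. It should be corrected because the correction is easy and concerns safety.

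**What to change.** Align 6.9 with 9.0:

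- Ask a cause-neutral question: any change in health, mood, sleep or alertness since the first dose, whatever the cause.
- Add brief prompts for the section 7.1 risks: new or worse voices or suspiciousness, thoughts of self-harm, irritability or hostility, low mood, somnolence, rash and infection.
- Record symptoms that are new or worse than at baseline as adverse events, so that stable pre-existing symptoms are not counted. Leave cause to the investigators on the section 9.0 scale.
- As a minor clarification, state a call window around the middle of dosing, in keeping with the section's title.

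The cost is a revised call script and a line on timing, a few more minutes on a call already planned, and more adverse event entries to review. The change does not touch treatment.
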